14.3 Tertiary/Exploratory Analysis

14.3.1 Central Nervous System (CNS) Tumor Response

Data used to perform the analyses described in the following sections will be provided by the vendor who performs the overall IRC tumor assessment and will be based on Response Assessment in Neuro-Oncology Brain Metastases (RANO-BM) criteria (Lin et al., 2015). This evaluation will not continue beyond the switch from monotherapy to combination treatment.

Unless stated otherwise, results from these analyses will be presented in tables and figures for all the participants in the combination arm from the FAS with baseline CNS metastases as defined below. Results from all the participants with baseline brain metastases will be listed.

CNS response may also be cited as "intracranial response".

14.3.1.1 Best Overall Response, Objective Response and Disease Control

Best Overall response (BOR) will be derived for all participants who undergo the brain evaluation perfomed by IRC following the RANO-BM criteria and for whom baseline CNS metastases were detected. Baseline CNS metastases are defined as metastases with "BRAIN" as location, either of target, enhancing non-target or non-enhancing non-target lesion. BOR will be derived based on IRC reported overall response assessments from the study treatment start date until documented disease progression, taking requirements for confirmation into account as detailed below.

BOR Based on Confirmed Responses:

- CR = at least two determinations of CR at least 4 weeks (28 days) apart (with no prior PD or PD in between)
- PR = at least two determinations of PR or better (PR followed by PR or PR followed by CR) at least 4 weeks (28 days) apart (and not qualifying for a CR), with no prior PD or PD in between
- SD = at least one SD assessment (or better) after the start date of study treatment with no prior PD (and not qualifying for CR or PR)
- Non-CR/non-PD (applicable only to participants without any target lesion at baseline) = at least one non-CR/non-PD assessment (or better) after start date without prior PD (and not qualifying for CR)
- PD = PD ≤ 90 days after start date of study treatment (and not qualifying for CR, PR, SD or Non-CR/non-PD as applicable)

• Not Evaluable (NE): all other cases

OR

Participants are defined as having an OR if they achieved either a confirmed BOR of CR or PR from first administration of study treatment to first observation of PD.

DC

Participants are identified as having objective DC if:

- They had a CNS target lesion at baseline and achieve a BOR of confirmed CR, PR or SD without prior PD
- They had only CNS non-target lesions at baseline and achieve a BOR of confirmed CR or non-CR/non-PD without prior PD

The number and proportion of participants with BOR of confirmed CR, confirmed PR, SD, Non-CR/non-PD, PD, and NE as well as the number and proportion of participants achieving OR and DC and the corresponding 2-sided exact Clopper-Pearson 95% CI will be presented. The number of participants with CNS baseline metastases (measurable and non-measurable disease) will be the denominator to derive percentages in this analysis.

Additionally, the number and proportion of participants with BOR of confirmed CR, confirmed PR, SD, PD, and NE as well as the number and proportion of participants achieving OR and the corresponding 2-sided exact Clopper-Pearson 95% CI will be tabulated for the subset of participants with target CNS baseline metastases (measurable disease). The number of participants with target CNS baseline metastases will be the denominator to derive percentages in this analysis.

A Spider plot will show the percent change in the sum of CNS target lesion diameters over time for each participant in the combination arm with target CNS baseline metastases who belongs to the mFAS. Different line patterns will distinguish time on and off-treatment.

In addition, a waterfall plot will show the percent change in sum of target lesion longest diameters between baseline and the best post-baseline assessment for each participant in the combination arm with target CNS baseline metastases who belongs to the mFAS. Different colours will illustrate the intracranial BOR.

For all the participants in the FAS who underwent this brain evaluation, data collected from the evaluation of the brain imaging and related response will be listed.

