Intracranial response (CR or PR) by IRC	Participants with brain metastases as target lesions are identified as having an intracranial response if they achieve either a confirmed CR or PR from first administration of study treatment to first observation of PD. Confirmation needs to take place by a tumor assessment at least 4 weeks (28 days) after the tumor assessments initially indicating CR or PR.

Endpoint	Definitions and Statistical Analysis Methods
	Intracranial response rate (confirmed CR or PR) and the corresponding 2-sided exact Clopper-Pearson 95% CI will be presented. The denominator for intracranial response rate will be the number of participants with brain metastases as target lesions.

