14.1 Primary Endpoint: Objective Response by IRC

14.1.1 Derivation and analysis

BOR will be assessed based on reported overall responses at different evaluation time points from the study treatment start date until documented disease progression in accordance with RECIST v1.1, taking requirements for confirmation into account as detailed below. Clinical deterioration will not be considered as documented disease progression. The date of the overall response assessment is the earliest date for imaging of target, non-target and new lesions of images taken at that response assessment.

BOR Based on Confirmed Responses:

- CR = at least two determinations of CR at least 4 weeks (28 days) apart (with no PD in between)
- PR = at least two determinations of PR or better (PR followed by PR or PR followed by CR) at least 4 weeks (28 days) apart (and not qualifying for a CR), with no PD in between
- SD = at least one SD assessment (or better) ≥ 12 weeks (84 days) after the start date of study treatment (and not qualifying for CR or PR)
- $PD = PD \le 90$ days after start date of study treatment (and not qualifying for CR, PR or SD)
- Not Evaluable (NE): all other cases.

There may be uncommon situations where the above rules might need further explanation. Some of these cases are listed below together with the BOR value that should be assigned:

- SD can follow PR only in the rare case that tumor increases by less than 20% from the nadir, but enough that a previously documented 30% decrease from baseline no longer holds. If this occurs, the sequence PR-SD-PR is considered a confirmed PR. A sequence of PR-SD-SD-PD would be a best response of SD if the minimum duration for SD definition has been met.
- When an unconfirmed PR or CR is assessed at least 12 weeks after the start date of study treatment with no PD before, the best response would be SD.
- When there is an assessment of SD, PR or CR within 12 weeks from the start of study treatment followed by a PD after 90 days, the best response would be NE.

Participants are defined as having an Objective Response (OR) if they achieved either a confirmed BOR of CR or PR according to RECIST v1.1 from first administration of study treatment to first observation of PD.

The OR rate (ORR) is the proportion of participants with OR in the analysis set.

No formal statistical hypotheses will be tested.

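### CNS disease control lacks the 12-week minimum that systemic disease control has, and the SAP moves the protocol's target-lesion intracranial response to an additional table without declaring it

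*SAP*

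**What the plan says.** SAP 14.3.1.1 defines CNS endpoints from the IRC's RANO-BM assessments.

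**Duration.** CNS SD requires "at least one SD assessment (or better) after the start date of study treatment with no prior PD". For participants with no target brain lesion, the corresponding category requires "at least one non-CR/non-PD assessment (or better) after start date without prior PD". Neither has a minimum time. Both count as CNS disease control; for the second group the rule reads "They had only CNS non-target lesions at baseline and achieve a BOR of confirmed CR or non-CR/non-PD without prior PD". By contrast, SAP 14.1.1 accepts systemic SD only from an assessment no earlier than "12 weeks (84 days) after the start date of study treatment". SAP 14.2.4 and Protocol 9.4.1 both define disease control as confirmed response or SD held for 84 days or more.

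**Population.** For the main CNS table, SAP 14.3.1.1 states: "The number of participants with CNS baseline metastases (measurable and non-measurable disease) will be the denominator". The estimand table in SAP section 14 agrees: its CNS population has any baseline brain lesion, and participants with target lesions appear only among the supplementary analyses. A second table in 14.3.1.1 gives best overall response and objective response for the target subset: "The number of participants with target CNS baseline metastases will be the denominator to derive percentages in this analysis". Disease control is not listed for that table. Protocol 9.4.1 states: "The denominator for intracranial response rate will be the number of participants with brain metastases as target lesions". SAP section 7, which lists changes from the protocol's analyses, does not mention the difference.

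**The concern.** Two endpoints called disease control would appear in one report under different rules, with the CNS rule the more lenient. A reader comparing the two rates could take a difference in definition for a difference in intracranial activity. Exclusion criterion 1 admits brain metastases that are asymptomatic, stable or off steroids, and allows radiosurgery completed two weeks before treatment. One early non-progressing brain scan may therefore partly reflect entry selection or earlier local treatment.

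On response, participants with only non-target brain lesions have no PR category open to them, yet they are in the denominator of the main table. That rate is not the one the protocol defines, and the SAP does not say so where a reader would look.

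**Working it through.** The documents state no sample size, rate or precision for any CNS endpoint, so there is no plan figure to reproduce. The check compares the rules and then illustrates size under assumptions.

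**1. The same course under both rules.** In both sections PD applies only if SD is not met, and only up to day 90.

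| Course | CNS BOR / disease control (14.3.1.1) | Systemic BOR / disease control (14.1.1, 14.2.4) |
|---|---|---|
| SD at week 6, PD by day 90 | SD / yes | PD / no |
| SD at week 6, next scan PD after day 90 | SD / yes | NE / no |
| SD at week 6, no later evaluable scan | SD / yes | NE / no |

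In participants with only non-target brain lesions, non-CR/non-PD takes the place of SD in the CNS column, with the same result.

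**2. Scan timing (Protocol 8.1: every 6 weeks, ± 7 days).** First scan: 42 ± 7 = days 35 to 49. Second scan: 84 ± 7 = days 77 to 91. Scheduled scans thus put a practical floor of 5 to 7 weeks under the CNS rule. SAP section 9 also admits unscheduled assessments, which can be earlier.

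**3. Size of the disease control gap.** Assume exponential CNS PFS with median m months and 30.4375 days per month (SAP 9.6). The lenient rule adds those who are progression-free at day 42 but not at day 84:

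S(42) − S(84), with S(d) = exp(−ln 2 × d / (30.4375 m))

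| Assumed median | S(42) | S(84) | Difference |
|---|---|---|---|
| 6 months | 0.853 | 0.727 | 12.6 points |
| 9 months | 0.899 | 0.809 | 9.1 points |
| 12 months | 0.923 | 0.853 | 7.1 points |

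Differences are taken before rounding. An assumed median of 3 months would give 19.8 points. Participants with no scan after week 6 (third row in step 1) are not in these figures and would add to them. As an invented count, 3 such participants among 30 move disease control from 18/30 = 60.0% (exact 95% CI 40.6 to 77.3) to 21/30 = 70.0% (50.6 to 85.3).

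Whatever the inputs, on the same denominator disease control without a minimum cannot be lower than disease control with one.

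**4. Direction of the denominator effect.** Let s be the share with target lesions. Then

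ORR(all CNS) = s × ORR(target) + (1 − s) × CR rate(non-target only)

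This is below ORR(target) whenever the non-target-only CR rate is below it. Assume ORR(target) = 50% and a CR rate of 10%:

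- s = 0.7: 0.7 × 0.5 + 0.3 × 0.1 = 38%
- s = 0.5: 0.5 × 0.5 + 0.5 × 0.1 = 30%

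With invented counts of 8 responders among 12 target participants and 2 CRs among 18 non-target-only participants, the target rate is 8/12 = 66.7% (34.9 to 90.1) and the all-CNS rate is 10/30 = 33.3% (17.3 to 52.8).

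**5. Would copying the 84-day rule work?** Not as it stands. A week-12 scan on days 77 to 83 is within schedule but fails the cut. SD at day 80 followed by PD at the week-18 scan (about day 126) would be NE under the 14.1.1 rules, and disease control would be lost despite about 18 weeks without documented progression.

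**The case against.** The strongest reply has four parts.

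- **No protocol rule on CNS disease control is broken.** The protocol's only intracranial endpoint is response; CNS disease control is an exploratory SAP addition. This stands. The CNS rule is lenient relative to the trial's own systemic endpoint of the same name, and no stronger statement is supported. The RECIST text in Protocol Appendix 7 speaks of a minimum SD interval of generally 6 to 8 weeks, and the scan schedule roughly supplies that, though the SAP rule does not require it.
- **The protocol's response analysis is still planned.** A reader might infer that it was dropped. It was not: SAP 14.3.1.1 tabulates it with exact confidence intervals. What remains is its lower rank, the absence of disease control from that table, and the silence in section 7. The SAP's modification history notes updated intracranial text and an expanded RANO-BM analysis, but does not name the denominator.
- **The wider population fits the protocol's exploratory objective,** which refers to known brain metastasis. That is fair for the objective, but the analysis text in Protocol 9.4.1 is specific to target lesions.
- **Early CNS progression will be visible elsewhere,** in the CNS PFS curves and the listings. True, but this does not make the two disease control rates comparable.

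A reader might also infer that the SAP's choices together flatter the drug. Step 4 contradicts this for response: the wider denominator would usually pull the rate down.

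**Conclusion.** The point holds as a minor one on an exploratory endpoint. The CNS disease control rule is more lenient than the systemic one for both SD and non-CR/non-PD. The direction is certain from the definitions. The size, about 7 to 13 points for median CNS PFS of 12 down to 6 months, is illustrative and rests on an assumed exponential curve and assumed medians.

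The main intracranial response in the SAP uses a different population from the protocol's, and the change is undeclared. This is a question of ranking and disclosure; the documents do not support calling it inflation of the response rate or loss of the protocol analysis. It would also be too strong to say that the week-6 SD, week-12 PD course is always PD systemically: after day 90 it is NE, although neither outcome is disease control.

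**What to change.** 1. **SAP 14.3.1.1, disease control.** Apply the 12-week requirement to both CNS SD and CNS non-CR/non-PD, with allowance for the 7-day window so that an on-schedule week-12 scan qualifies (an assessment on or after day 84 − 7 = 77). State the allowance, because 14.1.1 uses a strict 84 days. Changing SD alone would leave non-target-only participants under the lenient rule. Alternatively, keep the current version labelled *any duration* and report a 12-week version beside it.
2. **SAP 14.3.1.1 and the estimand table, response.** Make the target-lesion table the main intracranial response, as in Protocol 9.4.1, and add disease control to it. Keep the all-CNS table as supplementary.
3. **SAP section 7.** List any departure from Protocol 9.4.1 that remains.

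The cost is SAP wording, one date condition, a change in the rank of two tables already planned, and one added endpoint in the target-lesion table. No new data are needed. The downside for the sponsor is that CNS disease control becomes less favourable.

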14.3.1.2 Duration of Response

The DOR will only be evaluated in participants with an OR (as defined in Section 14.3.1.1).

DOR is the time from when the CR/PR (whichever is first) criteria are first met until CNS PD or death due to any cause, within 126 days of the last evaluable tumor assessment, whichever occurs first (see Eisenhauer EA, et all 2009) (i.e., date of PD/death - date of last evaluable tumor assessment \leq 126).

DOR data will be censored on the date of the last evaluable tumor assessment for participants who do not have an event (PD or death) or for participants with an event more than 126 days after the last evaluable tumor assessment (i.e. date of PD/death - date of last evaluable tumor assessment > 126).

The last evaluable tumor assessment is defined as the last CNS tumor assessment result that is not "NE".

Kaplan-Meier estimates (product-limit estimates) will be presented together with a summary of associated statistics. In addition, a swimmer plot will be produced to present the time and duration of response. See Section 14.2.3 for more details.

14.3.1.3 **Progression Free Survival**

PFS time is defined as the time (in months) from first administration of study treatment to the date of the first documentation of CNS PD or death due to any cause within 126 days of the last evaluable CNS tumor assessment, whichever occurs first (i.e., date of PD/death - date of last evaluable tumor assessment ≤ 126).

The PFS data will be censored on the date of the last evaluable CNS tumor assessment for participants who do not have an event (PD or death) or for participants with an event more than 126 days after the last evaluable CNS tumor assessment (i.e. date of PD/death - date of last evaluable tumor assessment > 126).

The last evaluable tumor assessment is defined as the last CNS tumor assessment result that is not "NE".

Participants who do not have an evaluable post-baseline CNS tumor assessment will be censored at the date of the start of study treatment unless death occurred within 126 days of the first dose of study treatment in which case the death will be considered an event.

If a participant has only not evaluable CNS tumor assessments prior to a PD which is within 126 days of the first dose of study treatment, the PD will be considered an event; if the PD is after the 126 days, the PFS will be censored at the date of first dose.

The censoring and event date options to be considered for the PFS are presented in Error! Reference source not found..

Table 9.	Date of event /	censoring definition	for PFS analysis
----------	-----------------	----------------------	------------------

Status		Censoring	Date of event / censoring
Progressed or	Within 126 days after last response assessment of CR, PR, SD, non- CR/non-PD or start of treatment	Event	Minimum (Date of PD, Date of death)
died	Otherwise	Censored	Date of last tumor assessment with outcome CR, PR, SD, non-CR/non- PD or date of the start of treatment, whatever is later

Neither progressed nor died	Censored	Date of last tumor assessment with outcome CR, PR, SD, non-CR/non- PD or date of the start of treatment, whatever is later
-----------------------------	----------	---

Kaplan-Meier estimates (product-limit estimates) will be presented together with a summary of associated statistics as described in Section 14.2.5.

15 Safety Analyses

The primary safety endpoint analysis will be performed on the SRIAS analysis set whereas the secondary safety endpoint analyses will be performed on the SAF analysis set. Results will be presented as described in Sections 8.1.1 and 8.1.2, unless stated otherwise.

Unless stated otherwise, for those participants in the monotherapy arm who switch to the combination treatment, any safety assessment such as laboratory test, vital signs, ECOG Performance Status, ECG collected after Period 1 (see Table 3) will not be presented in tables (either summary or shift tables) or figures but only listed. Any change from baseline or percent change from baseline will be calculated using the baseline of Period 1.

The safety analyses will be done purely descriptively.

15.1 Primary Endpoint: Occurrence of DLTs during Cycle 1 of the Safety Run-In Period

The number and percentage of participants in the SRIAS analysis set with no DLT, 1 DLT or 2 or more DLTs observed during the DLT observation period (21 days after start of study treatment) will be tabulated together with the respective SOCs and PTs as well as the number of participants with any treatment emergent adverse event (TEAE) during Cycle 1. See Section 8.1 for the definition of DLT.

All relevant data for DLTs will also be listed.

15.2 Secondary Endpoints

15.2.1 Adverse Events

Adverse events will be coded according to the Medical Dictionary for Regulatory Activities (MedDRA) version (latest version at the time of database lock for each analysis; will be specified in outputs). Severity of AEs will be graded using the NCI-CTCAE (Version 5.0) toxicity grades.

Relationship with the study treatment components are collected in the "Adverse Events Details" eCRF page. Adverse Events can be related to tepotinib, osimertinib or both, depending on the treatment arm and period (see Table 3). As a general rule, if the relationship information is missing for a study treatment component, the AE will be considered as related to that component. On the other hand, if for a participant that belongs to the monotherapy arm and has switched, the AE

started or changed in toxicity grade in Period 1 and the relationship is missing for osimertinib, the AE will be considered as unrelated to osimertinib.

Incomplete AE-related dates will be handled as specified in Section 9.9.

TEAEs are those events that started during the on-treatment periods (see Section 9.3), or before Period 1 and worsened during the on-treatment periods. This includes also AEs ongoing at baseline, which first improve under study treatment and then worsen irrespective of baseline. The rules defined in Table 10 will be used to assign TEAEs to the on-treatment periods. Any AE occurring before Period 1 and resolved before Period 1 or not worsening during the on-treatment periods will be included in the AE listings, but will not be included in the TEAE summary tables (unless otherwise stated). Adverse events with changes in toxicity grade are recorded as separate entries in the eCRF with associated end and start dates (start date equals end date of previous entry, supported in eCRF by 'AENEWID' in SUPPAE). Records of the same AE will be considered as one event in the analysis. These events will be kept as separate records in the database in order to maintain the full detailed history of the events. In AE listings, records that are part of the same AE will be grouped together and presented in chronological order. If the severity of the reported event worsens after start of treatment, the TEAE flag will be re-evaluated for the worse and the subsequent records as per the TEAE definition: once one record is considered treatment emergent, all the subsequent records will be considered treatment emergent too, even if starting after the ontreatment periods.

All analyses described in Sections 15.2.2 and 15.2.3 will be based on TEAEs belonging to Period 1, if not otherwise specified. The AE listings will include all AEs (whether treatment emergent or not). A flag will be added to indicate if the AE is treatment emergent and in which period.

Unless otherwise specified, TEAEs will be summarized by number and percentage of participants with the TEAE in the category of interest and sorted by primary SOC and PT in alphabetic order.

Each participant will be counted only once within each SOC or PT. If a participant experiences more than one AE within an SOC or PT for the same summary period, only the AE with the strongest relationship or the worst severity, as appropriate, will be included in the summaries of relationship and severity.

Table 10.	Assignment of TEAEs to the on-treatment periods

	TEAE in Period 1	TEAE in Period 2
Starts before Period 1 and worsens during Period 1	Х	
Starts before Period 1 and worsens during Period 2		Х
Starts in Period 1 (regardless of worsening in Period 2)	Х	
Starts in Period 2		Х

15.2.2All Adverse Events

Adverse Event information is collected on the "Adverse Events Details" eCRF page.

Adverse events will be summarized by worst severity (according to NCI-CTCAE version 5.0) per participant, using the latest version of MedDRA PT as event category and MedDRA primary SOC body term as Body System category.

In case a participant has events with missing and non-missing grades, the maximum of the nonmissing grades will be displayed. No imputation of missing grades will be performed.

The overall summary of AEs table will include the frequency (number and percentage) of participants with each of the following:

- TEAEs
- Study treatment related TEAEs (any study treatment and by study treatment components)
- Serious TEAEs
- Study treatment related serious TEAEs (any study treatment and by study treatment components)
- TEAEs with NCI-CTCAE Grade \geq 3 and \geq 4
- Study treatment related TEAEs with NCI-CTCAE Grade ≥ 3 and ≥ 4 (any study treatment and by study treatment components)
- TEAEs leading to death
- Study treatment related TEAEs leading to death (any study treatment and by study treatment components)
- Adverse Events of Special Interest (AESIs)

Adverse events of special interest are defined as events suggestive of drug-induced liver injury including hepatic / liver failure and hepatitis (non-infectious). Adverse Events of Special Interest (AESI) will be identified according to a pre-specified search list provided by the Sponsor Safety Lead using the last available version of MedDRA Preferred Terms at the time of each analysis.

In addition, the following tables summarizing the frequency of participants with TEAEs by SOC and PT will be produced:

- TEAEs
- Study treatment related TEAEs (any study treatment and by study treatment components)
- Serious TEAEs
- Non-serious TEAEs applying a frequency threshold of 5%
- Study treatment related serious TEAEs (any study treatment and by study treatment components)
- TEAEs by worst NCI-CTCAE Grade (Any, ≥ 3 , ≥ 4 and 5)
- Study treatment related TEAEs by worst NCI-CTCAE Grade (Any, ≥ 3 , ≥ 4 and 5) (any study treatment and by study treatment components)

- TEAEs leading to death
- Study treatment related TEAEs leading to death (any study treatment and by study treatment components)
- Adverse Events of Special Interest (AESIs)

Participant listings of AE details collected on the "Adverse Events Details" eCRF page will also be provided:

- AEs
- AESIs
- Serious TEAEs

The overall AE summary table as well as the TEAEs by SOC and PT table will be repeated if there are at least 6 participants in the monotherapy arm who switch to the combination treatment. For these tables, all TEAEs from both Period 1 and Period 2 (see Table 10) will be considered. Results will be presented overall, i.e. there will be no split by MET amplification test result.

